### Positive psychology self-management intervention:

Recent studies have demonstrated the efficacy of positive psychology self-interventions in the management of chronic pain [18-20]. Our intervention (Table 2) will be modeled on the program used by Moskowitz and colleagues, who have demonstrated efficacy of their intervention in numerous randomized clinical trials for a myriad of conditions including substance use and pain [40-43]. Patients will receive instruction on how to complete the intervention during their initial visit. During the skill acquisition phase (scheduled for the first 5 weeks of the intervention), participants work through the interventions according to the schedule and will be asked to record their progress into a trial logbook. If participants are unable to meet, need to cancel a session, or require some additional time to acquire a skill, the skill will be covered in the next session. Once participants finish the skills acquisition phase, they will enter the habit solidifying phase for the remainder of their 12 week intervention period.

During the habit solidifying phase, patients will be encouraged to incorporate a positive psychology technique into their daily routine, with the goal of forming a habit [44]. Progress in habit formation will be assessed during the scheduled weekly peer check-in sessions.

### Telecare Intervention

We will utilize an evidence-based telecare approach to facilitate symptomatic management. We have successfully utilized this technique to manage pain, depression, and anxiety in several previous trials (Table 1). The telecare intervention consists of two main parts (1) symptom monitoring and (2) peer coach-facilitated treatment support.

During the trial, a peer coach will contact patients weekly by telephone (with or without video) to discuss how they are doing. Patients will be encouraged to share their logbook information with peers to facilitate discussion. Peer coaches will provide reinforcement and accountability for patients to keep up their symptom and positive psychology intervention logging. If patients report new or worsening symptoms, peer coaches will discuss with patients whether they have been able to use the treatments suggested at the trial start and will provide reminders to use these treatments if warranted. If the patient reports elevated distress, intolerance of symptomatic treatments, opioid cravings or opioid use disorder behaviors, the peer and participant will relay this information to the physician-investigator. If an adjustment to the treatment plan is indicated, the physician-investigator will make adjustments in collaboration with the patient's primary treating physician.

The peer coach will meet with the study PI ([name]) weekly to discuss new cases and treatment plans as well as participants for whom treatment adjustments based upon symptom monitoring may be warranted.

### Usual care arm:

Patients randomized to usual care will continue to receive care from their primary physician, with no active involvement by study personnel. Patients in this group will fill out the same baseline and 12 week questionnaires as patients in the intervention arm.

**Outcome measures.** In addition to demographic and clinical characteristics that will be assessed at baseline, numerous symptom measures will be assessed at baseline and at the conclusion of 3 months of treatment (Table 3). Participants will receive a \$40 gift card for each of the two outcome interviews (baseline and conclusion) that they complete. Opioid daily dose reduction is the primary outcome and will be measured in morphine-equivalent daily dose (MEDD). Secondary outcomes will include pain intensity, pain interference, positive affect, depression, anxiety, and disability. We will attempt to collect follow-up questionnaire data for up to 3 additional months after the conclusion of the trial to maximize the likelihood of data capture.

**Qualitative Interview.** At the conclusion of the study, participants will be invited to participate in semi-structured individual interviews to discuss their experience with chronic pain and the trial, what worked well, what could be improved, and potential strategies to bolster recruitment of additional patients in future studies. We will aim to conduct interviews of 10 patients in the intervention arm. Each interview will be audiotaped, transcribed, and independently analyzed by 2 reviewers to determine key themes related to barriers and facilitators using qualitative methods used in previous trials by [name] [49, 50]. Participants will receive a \$50 gift card for completion of a qualitative interview.

**Data Analysis Plan.** Descriptive statistics (means, medians, standard deviations, inter-quartile ranges, and frequencies) will be computed to assess variables' distributional properties and to describe the sample when disseminating results. Since this is a small pilot study to test feasibility and patient acceptance, it is not formally powered to test a specific treatment effect size. Instead, whatever treatment effect is found will be useful in planning the sample size for a more definitive trial. However, a sample of 20 participants per arm has 80% power with an alpha of .05 to detect a 30 mg MEDD greater dose reduction in the intervention group (e.g., from 70 MMED to 40 MMED) assuming a SD for the MEDD of 30[8] and 20% attrition (i.e., 32 of the 40 participants completing the trial). We will also explore treatment effect moderators, including medical comorbidity (using a 9-item checklist), personality (TIPI scores), baseline pain interference, pain catastrophizing, pain self-efficacy, baseline somatic symptoms (SSS-8), mental health (PROMIS depression and anxiety), and baseline opioid difficulties (PODS).

**Feasibility.** Several factors support the feasibility of our trial. First, as noted in the Preliminary Work section (**Table 1**), our team has successfully conducted multiple telecare-centered intervention trials [8, 13, 15, 25-33, 51]. Second, several of these trials have demonstrated efficacy in managing pain [8, 13, 15, 25-33, 51]. Third, we will be utilizing a positive psychology intervention that has been shown to improve pain outcomes in patients with chronic pain [42]. Finally, others have demonstrated success in recruiting patients for and completing an opioid tapering program [17, 35]

**Potential Problems and Alternative Approaches.** As described above, should patient recruitment prove challenging, we have several recruitment strategies. Further, adding additional clinical sites for recruitment would be another potential approach. High drop-out rates are an additional concern. If this occurs, identifying factors contributing to drop-out can inform further refinement of the treatment protocol in a subsequent study.

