**Table 3. Outcome Assessment: Measures and Schedule of Administration**

Domain	Measure	# Items	Schedule (month)	
			0	3
Primary outcome				
Opioid Daily Dose	Morphine-Equivalent Daily Dose (MEDD).	1	X	X
Secondary outcomes				
Pain	PROMIS Pain	9	X	X
Pain Catastrophizing	CSQ Catastrophizing	4	X	X
Pain Efficacy	Pain Self Efficacy Questionnaire (PSEQ)	4	X	X
Depression, Suicidality	PROMIS Depression / *P4 Screener	5	X	X
	Remission Evaluation and Mood Inventory Tool (REMIT)	5	X	X
Anxiety	PROMIS Anxiety	4	X	X
Positive Affect	Positive and Negative Affect Scale – Short Form (PANAS – SF)	10	X	X
Somatic Symptoms	Somatic Symptom Scale – 8 (SSS8)	8	X	X
Disability	Sheehan Disability Scale (SDS)	3	X	X
Opioid Problems	Prescription Opioids Difficulties Scale (PODS)	16	X	X
	PROMIS Prescription Opioid	7	X	X
	Craving State, OUD Intensity/Interference Scale (ORG)	4	X	X
Substance Use	Substance Use Questionnaire	13	X	
Medical Co-Morbidity	Chronic disease checklist	9	X	
Demographics		8	X	
Personality	Ten Item Personality Inventory (TIPI)	10	X	X
Global Rating of Change		2		X
Satisfaction with treatment		2		X

Interview time in minutes (est.)			45	45
----------------------------------	--	--	----	----

\*P4 screener only used at baseline

**Benchmarks of Success.** The following will provide benchmarks to evaluate the success of the proposed study: (1) Secure IRB approval for the study; (2) Recruit and consent the first 20 participants, conduct the interventions with these participants, and collect data; (3) Repeat with the second set of 20 participants; (4) Enter and clean the data; (5) Analyze data; (6) Write manuscript(s) and submit for publication; and (7) Develop an NIH K-23 grant application based on results of this trial.

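### The 80% power figure uses the SD of the dose for an outcome defined as a dose reduction; compared as a raw change, it holds only if the month-0 to month-3 correlation is about 0.5 or higher, and no primary model is named

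*Combined protocol and SAP*

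**What the plan says.** In section D. APPROACH, the Outcome measures paragraph states: "Opioid daily dose reduction is the primary outcome and will be measured in morphine-equivalent daily dose (MEDD"). Table 3 lists "Morphine-Equivalent Daily Dose (MEDD") as the only primary measure, collected at months 0 and 3.

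The Data Analysis Plan says that the pilot was not sized for a particular effect and that the observed effect will help to size a later trial. It nevertheless puts power at 80%, at the .05 level and with 20 patients per arm, for a difference described as a "greater dose reduction in the intervention group (e.g., from 70 MMED to 40 MMED) assuming a SD for the MEDD of 30". The size of that difference is 30 mg. The calculation allows for one patient in five dropping out, which leaves 32 completers.

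Apart from descriptive statistics and exploratory moderators, it describes no analysis. It does not say whether the arms will be compared on change in dose, on month-3 dose, or on month-3 dose adjusted for month-0 dose. It gives neither an SD of change nor a correlation between the two visits.

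**The concern.** The effect is worded as a difference in reductions, but the SD beside it is that of a single dose measurement. A reduction is the difference of two measurements on the same person, and its spread depends on how strongly they are correlated. If the correlation is low, the SD of a reduction is well above 30 and power is well below 80%.

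A low correlation is possible here. The Opioid Reduction section makes dose reduction optional and negotiated, so some intervention patients may come down a long way and others not at all.

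Two things are at stake. The three candidate analyses differ in power, and with none named, the choice could be made after the data are seen. The results are also meant to plan a definitive trial, and using an SD of levels for an outcome that is a change would carry the mismatch into that calculation.

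**Working it through.** **Inputs from the Data Analysis Plan:** difference 30 mg, SD of MEDD 30, alpha .05, 32 completers, so 16 per arm under the 1:1 allocation in Study Design. Sidedness is not stated. Two-sided is assumed because it reproduces the figure; one-sided gives 88%.

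**Assumed:** SD 30 at both visits and in both arms, and r from 0 to 0.7.

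**1. The plan's own figure.** Treat 30 as the SD of whatever is compared.
- SE = 30 × √(2/16) = 10.61, and 30/10.61 = 2.83.
- Normal approximation: Φ(2.83 − 1.96) = 80.7%.
- Non-central t with 30 df: 78.1%.

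The 80% therefore reproduces if 30 is the SD of the quantity analysed.

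**2. Raw change score.** SD of change = 30 × √(2(1 − r)), which equals 30 only at r = 0.5. Power is by non-central t, 30 df, with non-centrality 30 / (SD × √(2/16)).

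**3. Month-3 MEDD adjusted for month-0 MEDD.** Residual SD = 30 × √(1 − r²). Estimating the baseline slope costs one df (29 remain) and inflates the SE by about √(1 + 1/28) = 1.018 on average.

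| r (assumed) | SD of change | Power, change score | Residual SD, adjusted | Power, adjusted |
|---|---|---|---|---|
| 0 | 42.4 | 49% | 30.0 | 77% |
| 0.3 | 35.5 | 64% | 28.6 | 80% |
| 0.5 | 30.0 | 78% | 26.0 | 87% |
| 0.7 | 23.2 | 94% | 21.4 | 96% |

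Simulation with ordinary standard errors and t critical values agrees with the adjusted column to within a point.

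**4. Break-even.** Change-score power reaches 80% at r = 0.49 (normal approximation) or 0.52 (t). Above that it exceeds 80%.

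**5. Why adjustment helps.** With equal SDs, the ratio of adjusted to change-score variance is (1 − r²) / (2(1 − r)) = (1 + r)/2. That is 0.65 at r = 0.3 and 0.75 at r = 0.5, before the small cost of estimating the slope.

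**6. Sensitivity of the adjusted figures.**
- With an HC3 robust standard error, simulated power is about 73% at r = 0 and 77% at r = 0.3, roughly 3 points lower than with the ordinary one.
- If month-3 SD is 40 in the tapering arm only (assumed), ordinary adjusted power is about 63%, 67% and 75% at r = 0, 0.3 and 0.5.
- If month-3 SD is 37.5 in both arms (assumed; normal approximation), adjusted power is 66% at r = 0.3 and 74% at r = 0.5. The change score then has 56% and 70%, so extra spread lowers both.

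**The case against.** The strongest reply is that the plan never commits to a change score. Under randomisation, the expected difference in reductions equals the expected difference in month-3 doses, and a plain comparison of month-3 MEDD with SD 30 gives 78% to 81%. On that reading the 80% is coherent. This stands: a reader might infer that the plan has chosen raw reductions, but the text names no estimator. It also leaves the gap in place, because the outcome is defined as a reduction and nothing says that month-3 dose is what will be compared.

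Second, r = 0 is an extreme case. Patients are on long-term daily opioids, usual care involves no active study contact, and the hypothesised effect is a percentage fall. All of this suggests a positive correlation. That is fair, and the 49% should be read as the end of a range. The documents give no value, however, and the shortfall at r = 0.3 is already 16 points against 80%.

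Third, the plan disclaims formal powering, and no decision rule depends on the figure. This lowers the weight of the point. It does not remove it, because the 80% is still stated and the observed effect is to be used for planning.

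Finally, chance baseline imbalance might be counted as a second defect. With 20 per arm, the SE of the baseline difference is 30 × √(2/20) = 9.5 mg, so a gap above 10 mg occurs in about 29% of trials. That variation is already part of the change-score variance in the table, and it is not a bias.

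**Conclusion.** The point stands in a limited form. The power sentence pairs an SD of the dose with a reduction in dose and leaves the primary model open. If raw reductions are compared, the stated power holds only at r of about 0.5 or higher; for r from 0 to 0.7 it runs from 49% to 94%. This rests on SD 30 at both visits, 16 completers per arm, a two-sided test and assumed values of r.

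Two stronger readings are not supported. One is that the 80% is simply wrong, or true only at r = 0.5 exactly: the risk is one-sided, and a month-3 comparison reproduces the figure. The other is that baseline adjustment guarantees 80% whatever the correlation: it gives about 77% at r = 0 even when the month-3 SD is 30, and clearly less if doses spread more in the tapering arm. Adjustment is still the better choice. With SD 30 at both visits it had higher power than the change score at every r examined, and the gain is largest where r is low. The change should be made, though nothing in a pilot of this kind fails without it.

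**What to change.** In the Data Analysis Plan, name the primary analysis as a linear model of month-3 MEDD on arm and month-0 MEDD, and say which standard error will be used. A robust one is reasonable if dose is expected to spread more in the tapering arm, but its power cost should be acknowledged.

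Replace the power sentence with wording such as:

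> SD 30 is the SD of the dose. Assuming SD 30 at month 3 in both arms, the baseline-adjusted comparison with 16 completers per arm has about 77% power for a 30 mg difference at r = 0, 80% at r = 0.3 and 87% at r = 0.5 (about 3 points less at these values with an HC3 robust standard error, and lower if month-3 dose spreads more in the tapering arm). An unadjusted reduction would have 49% to 94% for r from 0 to 0.7.

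Report the observed r and the residual SD, since the next trial needs both. The cost is a few sentences and one degree of freedom. Month-0 MEDD is already scheduled for collection in Table 3, so no new data are needed.

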**Table 3. Outcome Assessment: Measures and Schedule of Administration**

Domain	Measure	# Items	Schedule (month)	
			0	3
Primary outcome				
Opioid Daily Dose	Morphine-Equivalent Daily Dose (MEDD).	1	X	X
Secondary outcomes				
Pain	PROMIS Pain	9	X	X
Pain Catastrophizing	CSQ Catastrophizing	4	X	X
Pain Efficacy	Pain Self Efficacy Questionnaire (PSEQ)	4	X	X
Depression, Suicidality	PROMIS Depression / *P4 Screener	5	X	X
	Remission Evaluation and Mood Inventory Tool (REMIT)	5	X	X
Anxiety	PROMIS Anxiety	4	X	X
Positive Affect	Positive and Negative Affect Scale – Short Form (PANAS – SF)	10	X	X
Somatic Symptoms	Somatic Symptom Scale – 8 (SSS8)	8	X	X
Disability	Sheehan Disability Scale (SDS)	3	X	X
Opioid Problems	Prescription Opioids Difficulties Scale (PODS)	16	X	X
	PROMIS Prescription Opioid	7	X	X
	Craving State, OUD Intensity/Interference Scale (ORG)	4	X	X
Substance Use	Substance Use Questionnaire	13	X	
Medical Co-Morbidity	Chronic disease checklist	9	X	
Demographics		8	X	
Personality	Ten Item Personality Inventory (TIPI)	10	X	X
Global Rating of Change		2		X
Satisfaction with treatment		2		X

Interview time in minutes (est.)			45	45
----------------------------------	--	--	----	----

\*P4 screener only used at baseline

**Benchmarks of Success.** The following will provide benchmarks to evaluate the success of the proposed study: (1) Secure IRB approval for the study; (2) Recruit and consent the first 20 participants, conduct the interventions with these participants, and collect data; (3) Repeat with the second set of 20 participants; (4) Enter and clean the data; (5) Analyze data; (6) Write manuscript(s) and submit for publication; and (7) Develop an NIH K-23 grant application based on results of this trial.

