**Collaborative Care is a healthcare model capable of providing specialty care to far more patients than can be achieved through traditional one-on-one treatment models.** Collaborative Care has proven effective in delivering treatments for managing depression and pain in primary care settings [12-15]. A few recent studies have also demonstrated efficacy in treating addiction and opioid dependence using a collaborative care approach [16, 17]. Several different pain interventions have been effective in these collaborative care trials, including medication optimization, cognitive behavioral therapy, and several different structured self-management programs. Recently, pain researchers have found positive psychology-based interventions to be effective, well-received, and easy to deliver [18-20], making this intervention well-suited to pair with collaborative care. In the proposed clinical trial, we will assess the feasibility of utilizing collaborative care to facilitate opioid tapering in patients with chronic pain using a positive psychology intervention.

**Primary Aim:** Determine the potential effectiveness of delivering Collaborative Care for reducing opioids in patients with chronic pain.

**Hypothesis:** Collaborative Care will be effective (30% reduction in mean morphine equivalent dose/day [MMED]) in reducing opioids while maintaining pain control (< 1 point increase in 0 to 10 pain rating scale).

**Secondary Aim:** Assess adherence to tapering and satisfaction of patients with this Collaborative Care approach.

**Hypothesis:** Patients will be satisfied with (mean score  $\geq 3$  on 0 to 5 satisfaction scale) and adhere to ( $\geq 70\%$  retention) the 12-week opioid tapering program.

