**Table 1. Previous Work by Team Relevant to CCODAP Trial**

Trial	[name] Role	N	Mo.	Symptoms Targeted	Patient Sample	Tele-care	Intervention	Benefits
AIM[25]	Co-PI	176	9	Depression	Neurology (stroke)	Partly	Medications	Intervention > Usual care
SCAMP[26, 27]	PI	250	12	Pain Depression	Primary care	Partly	Medications & Self-management	Intervention > Usual care
INCPAD[13, 28]	PI	405	12	Pain Depression	Cancer (all types)	Fully	Medications	Intervention > Usual care
SCOPE[14, 29]	PI	250	12	Pain	Primary care	Fully	Medications	Intervention > Usual care
CAMMPS[15, 30]	PI	300	12	Pain, Anxiety, Depression	Primary care	Fully	Medications & Self-management	NCM + ASM > ASM alone†
COPE[31, 32]	Co-Invest	495	6	Function Pain	Cancer (advanced)	Partly	Physical therapy & Pain management	Intervention > Monitoring only
SPACE[8, 33]	Co-Invest	240	12	Pain	Primary care	Partly	Medications	Non-opioids = Opioids
ESCAPE[34]	Co-Invest	241	9	Pain	Primary care	Partly	Medications + CBT	Intervention > Usual care

† NCM = nurse care management, ASM = automated symptom management

**Study Design.** Forty patients with non-cancer chronic pain on long-term oral opioid therapy will be recruited into this pilot trial. Patients will be randomized to receive either the treatment intervention (n = 20) or usual care (n = 20). Assignment to treatment arm will be determined by a computer-generated randomization list in permuted blocks of 4 to maintain balanced assignment throughout the trial. Participants must: (1) be age 18 or older, (2) have an established chronic pain disorder of at least 6 months, and (3) be receiving chronic daily oral opioid treatment. Exclusion criteria are: (1) not speaking English, (2) significant cognitive impairment that would hinder participation.

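### Satisfaction is asked only at month 3 and nothing is scheduled when a participant stops, so both parts of the secondary hypothesis can be met while the intervention-arm mean is below 3

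*Combined protocol and SAP*

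**What the plan says.** All places are in the combined protocol and SAP.

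- **Specific Aims, Secondary Aim.** The hypothesis has two parts joined by *and*: a mean satisfaction score of at least 3 "on 0 to 5 satisfaction scale", and at least 70% retention in the 12-week programme.
- **Table 3.** "Satisfaction with treatment" has 2 items, marked at month 3 and not at baseline. No assessment is tied to stopping the programme, and no item records a reason for stopping.
- **Outcome measures.** There is provision for late capture: "We will attempt to collect follow-up questionnaire data for up to 3 additional months after the conclusion of the trial".
- **Qualitative Interview.** "At the conclusion of the study, participants will be invited to participate in semi-structured individual interviews". The aim is 10 interviews in the intervention arm. Neither completers nor those who stopped are singled out.
- **Data Analysis Plan.** Power assumes 20% attrition, with 32 of 40 completing. No analysis set, denominator or missing-data rule is given for satisfaction.
- **Potential Problems and Alternative Approaches.** If drop-out is high, "identifying factors contributing to drop-out can inform further refinement of the treatment protocol in a subsequent study".

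**The concern.** A score taken once, at the end, is missing most often for people who have left, and people who leave are plausibly less satisfied than those who stay. With no stated denominator, the default is a mean over whoever answers. That mean is likely to run high as a measure of acceptability for the arm as randomised.

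Acceptability matters here. The Data Analysis Plan describes the study as a pilot of feasibility and patient acceptance, and its results are to support a K-23 application. Reasons for leaving are what the next design would most need, and the plan says it wants them, yet no scheduled item asks for them directly.

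**Working it through.** **Inputs from the documents**
- Intervention arm: 20 (Study Design).
- Satisfaction threshold 3 on 0 to 5; retention threshold 70%, so 0.70 × 20 = 14 (Specific Aims).
- Attrition 20%, 32 of 40, so 16 per arm if equal in both arms (Data Analysis Plan).

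**Assumptions**
- The non-respondent mean *d* is not in the documents; 0 to 3 is shown.
- The number responding equals the number retained.
- The 2 items yield one score on the 0 to 5 scale; the documents do not say how.

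**Step 1: the plan's own figure.** The only sample-size figure is 80% power for the primary outcome. The difference of 30 mg over an SD of 30 gives a standardised effect of 1.0. With 16 per arm and two-sided alpha 0.05 (sidedness is not stated), 1.0 × √(16/2) − 1.96 = 0.868, or 80.7% power by the normal approximation; a t-test gives 78.1%. The figure reproduces with 16 per arm. With all 20 it would be 88.5%. The plan's arithmetic therefore expects no month-3 outcome from about 4 per arm. No precision is stated for satisfaction.

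**Step 2: whole-arm mean.** With *r* respondents averaging *m*:

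whole-arm mean = (*r* × *m* + (20 − *r*) × *d*) / 20

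At *m* = 3.0:

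| Responding | d = 0 | d = 1 | d = 2 | d = 3 |
|---|---|---|---|---|
| 14 of 20 | 42/20 = 2.1 | 48/20 = 2.4 | 54/20 = 2.7 | 60/20 = 3.0 |
| 16 of 20 | 48/20 = 2.4 | 52/20 = 2.6 | 56/20 = 2.8 | 60/20 = 3.0 |

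**Step 3: respondent mean needed for a whole-arm mean of 3.** This is (60 − (20 − *r*) × *d*) / *r*.
- 14 responding: 60/14 = 4.29 if *d* = 0; 54/14 = 3.86 if *d* = 1.
- 16 responding: 60/16 = 3.75 if *d* = 0; 56/16 = 3.50 if *d* = 1.

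**Step 4: when the whole arm falls below the scale midpoint of 2.5.** With respondents at exactly 3.0, non-respondents must average below (50 − 3*r*) / (20 − *r*).
- 14 responding: 8/6 = 1.33.
- 16 responding: 2/4 = 0.5.
- With 14 responding and a respondent mean above 50/14 = 3.57, it cannot happen at all.

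**Step 5: reasons for leaving.** Set beside the stated wish to identify what contributes to drop-out, Table 3 offers baseline measures (opioid difficulties, catastrophizing, self-efficacy, mood, personality) on which leavers and stayers can be compared. It offers no direct question on why a participant stopped.

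**The case against.** Several objections have force.

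- **Completers only.** A reader might infer that satisfaction and interviews are restricted to people who finish. The documents do not say so. Table 3 gives a time point, the interview invitation is to participants, and questionnaires are pursued for up to 3 more months. Missed sessions roll forward and dose reduction is the patient's choice, so neither a missed session nor a decision not to taper removes anyone from assessment. Reliance on completers is a likely result of drop-out, not a rule. This objection stands, but late capture still leaves no rule for scores that never arrive.
- **Retention is part of the same hypothesis.** It counts leavers directly and limits them to 6 of 20 when the hypothesis is met. This stands, and the 14-of-20 figures are at that limit. It limits the gap without closing it.
- **A dissatisfied arm.** A reader might infer that the hypothesis could be met by an arm that is dissatisfied overall. Step 4 shows that this needs respondents close to the threshold and very low scores among the missing, and the 2.5 cut is itself an assumption. A mean below 3 is all that the figures support in general.
- **Interviews.** They do not enter the satisfaction mean. Who accepts an interview affects the qualitative findings only.
- **Scoring the missing as 0.** Basing the satisfied statement on this would count drop-out twice, since retention already penalises it, and at 14 of 20 would move the respondent mean required from 3 to 4.29. It is not recommended as the success rule.
- **Limited consequence.** The pilot is not formally powered and the Benchmarks of Success do not include this threshold. That keeps the point minor.

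**Conclusion.** The point holds as a cheap improvement to the measurement of the Secondary Aim. Satisfaction has one scheduled assessment, no stated denominator and no rule for missing scores, so a respondent mean of 3.0 with 70% retention meets the hypothesis while the whole-arm mean may be anywhere from 2.1 upwards. At the plan's own 20% attrition the floor is 2.4. The shortfall depends entirely on what non-respondents would have said: any average below 3 produces one when respondents are exactly at the threshold, an average of 3 produces none, and a respondent mean comfortably above 3 absorbs part or all of it. The figures also assume that those who stop are those who do not answer, which is likely but not laid down in the plan. Separately, the plan's intention to understand drop-out has no direct question behind it.

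**What to change.** 1. **Table 3.** Add an assessment at stopping for intervention participants: the 2 satisfaction items and one reason-for-stopping question, asked by phone or through REDCap. Keep month 3 for everyone still reachable. State in advance which score counts when a participant has both.
2. **Data Analysis Plan.** State that the satisfaction mean is taken over all intervention participants with a score. Report beside it the number missing and a sensitivity range for the missing scores, for example 0 to 3. Leave the threshold of 3 unchanged.
3. **Qualitative Interview.** State that invitations include participants who stopped. No fixed quota is needed.

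The cost is three short questions for those who stop and one extra line of analysis; the number of interviews does not change. Weekly telephone contact and REDCap are already in the protocol, though someone who no longer takes calls may still be missed. The drawbacks are that scores will be taken at different times and the reported satisfaction figure may be less favourable.
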